Version 3.0 Page 7 of 29

2. Glossary

Refer to the Optimize PRO parent protocol for a glossary of terms.

3. Synopsis

Title	Optimize PRO – FX Addendum	
Devices	Medtronic Evolut™ FX TAV System	
Sponsor	Medtronic Structural Heart Clinical Research	
FX Addendum Principal Investigator	[name]	
Product Status	Only commercially approved product will be used.	
Study Objective	The purpose of this addendum is to collect post-market clinical evidence on valve performance and procedural outcomes associated with the Evolut FX Device.	
Primary Endpoint	Rate of all-cause mortality or all-stroke at 30 days	
Secondary Endpoints	Median days from index procedure to discharge	
	 Percentage of subjects with ≥ moderate aortic regurgitation (AR) at discharge 	
	Rate of pacemaker implant for new onset or worsening conduction disturbance at 30 days	
	Percentage of subjects with a Non-Coronary Cusp (NCC) depth of implant between 1.0 and 5.0 mm	
	 Percentage of subjects with a canting absolute value NCC – Left Coronary Cusp (LCC) of ≤ 2.0 mm 	
Additional Exploratory	30-day and 1-year hospital re-admission rates	
Endpoints	1-year composite of all-cause mortality or all-stroke	
	Percent of patients with a major vascular complication	
	Percent of patients that require a recapture or resheath of the TAV	
	Percent of patients in which the target depth of implant was achieved	
	Orientation of valve relative to native anatomy	
Study Design	Post-market, multi-center, prospective, non-randomized	
Sample Size	Approximately 10 sites in the United States with approximately 150 subjects	

[figure not shown]
Version 3.0 Page 8 of 29

Patient Population	Subjects with severe, symptomatic aortic stenosis (AS) necessitating valve replacement		
Duration	Fotal addendum duration is estimated to be 24 months (time from first subject implanted to one-year follow-up on last subject mplanted)		
Key Inclusion Criteria	Acceptable candidate for treatment with the Evolut FX system in accordance with the Instructions for Use and local regulations		
	Subject is symptomatic from his/her aortic valve stenosis, as demonstrated by New York Heart Association (NYHA) Functional Class II or greater		
	Subject and the treating physician agree that the subject will return for all required post procedure follow-up visits		
	Anatomically suitable for transfemoral TAVR with the Medtronic TAVR system		
	Subject meets the legal minimum age to provide Informed Consent based on local regulatory requirements		
Key Exclusion Criteria	Contraindicated for treatment with the Evolut™ FX system in accordance with the Instructions for Use		
	 Anatomically not suitable for the Evolut™ FX system 		
	Previous aortic valve replacement		
	Reduced ventricular function with left ventricular ejection fraction (LVEF) < 35% as measured by resting echocardiogram		
	Frailty assessments identify:		
	 Subject is <80 years of age and three or more of the following apply; OR subject is ≥ 80 years of age and two or more of the following apply 		
	Wheelchair bound		
	 Resides in an institutional care facility (e.g., 		
	nursing home, skilled care center)		
	■ Body Mass Index <20kg/m²		
	■ Grip strength <16kg		
	Katz Index score ≤4Albumin <3.5 g/dL		
	Bicuspid valve verified		
	annulus and horizontal plane/vertebrae) > 70°		
	Implanted with pacemaker or ICD		
	Prohibitive left ventricular outflow tract calcification		

Medtronic Business Restricted

Version 3.0 Page 9 of 29

	 Estimated life expectancy of less than 12 months due to associated non-cardiac co-morbid conditions Other medical, social, or psychological conditions that in the opinion of the Investigator precludes the subject from appropriate consent, adherence to the protocol required follow-up exams Currently participating in an investigational drug or another device trial (excluding registries)
	 Need for emergency surgery for any reason Subject is less than legal age of consent, legally incompetent, or otherwise vulnerable
Study Procedures and Assessments	 Clinical assessment at baseline, discharge, 30 days, and 1 year Transthoracic echo at baseline, discharge, and 1 year Multi-Detector Computed Tomography at baseline and anytime post-procedure through the 30-day visit (contrast required for post-procedure CT) Quality of Life pre- and post-procedure, 30 days, and 1 year 12-lead ECG at pre- and post-procedure, discharge, 30 days, and 1 year

4. Introduction

Parent Study 4.1.

[figure not shown]
The Optimize PRO Clinical Investigation Plan (Parent protocol or Parent CIP) is the governing document for this addendum. Always refer to the most recent version of the parent protocol for details not described within this addendum. The purpose of this addendum is to provide details and requirements unique to participation in the FX addendum portion of the study.

Purpose 4.2.

The purpose of this addendum is to collect post-market clinical evidence on valve performance and procedural outcomes associated with the Evolut FX Device.

Version 3.0

Page 10 of 29

5. Objective and Endpoints

5.1. Objective

The purpose of this addendum is to collect post-market clinical evidence in the United States, on valve performance and procedural outcomes associated with the Evolut FX Device.

5.2. Endpoints

The following endpoints will be used to evaluate valve performance and procedural outcomes associated with the Evolut™ FX System.

5.2.1. Primary Endpoint

The primary endpoint is the rate of all-cause mortality or all stroke at 30 days.

5.2.2. Secondary Endpoints

The following are the secondary endpoints:

- Median days from index procedure to discharge
- Percentage of subjects with ≥ moderate aortic regurgitation (AR) at discharge
- Rate of pacemaker implant for new onset or worsening conduction disturbance at 30 days
- Percentage of subjects with an NCC depth of implant between 1.0 and 5.0 mm
- Percentage of subjects with an absolute canting value |NCC-LCC| of ≤ 2.0 mm

5.2.3. Additional Exploratory Endpoints

The following are additional exploratory endpoints:

- 30-day and 1-year hospital re-admission rates
- 1-year composite of all-cause mortality or all-stroke
- Percent of patients with a major vascular complication
- Percent of patients that require a recapture or resheath of the TAV
- Percent of patients in which the target depth of implant was achieved
- Orientation of valve relative to native anatomy

5.2.4. Rationale

The basis for the selection of these study endpoints include:

Clinically relevant outcomes of the Evolut[™] FX System

Medtronic Business Restricted

Version 3.0

Page 11 of 29

- Objectively defined and measurable in the majority of subjects
- Consistent with current recommendations for endpoints in TAVR clinical studies⁽¹⁾

6. Study Design

This is a post market, multi-center, prospective, non-randomized study. The study methods include the following measures to minimize potential sources of bias:

- An external, independent Clinical Events Committee (CEC) will review and adjudicate, at minimum, all deaths and endpoint related adverse events. Safety endpoint results will be based on CEC adjudications.
- All sites will follow a standardized protocol for acquisition of echocardiographic endpoint data.
- Core labs will evaluate all echocardiograms; echocardiographic trial endpoint results will be based on Core Lab assessments.
- Subjects will be screened to confirm eligibility for enrollment with pre-defined inclusion and exclusion criteria.

6.1. Duration

The enrollment period is estimated to be approximately 12 months and subjects will be followed for one year post index procedure; therefore, the estimated total duration of the addendum (first subject enrolled to last subject completing his/her last follow-up exam) is estimated to be approximately 24 months.

6.2. Study Oversight

Refer to the Optimize PRO Parent Protocol for details of study oversight.

6.3. Trial Organization

Refer to the Optimize PRO parent protocol for details on participating site requirements, site principal investigators (PIs), site heart teams, the publications committee, and trial training.

7 Product Description

7.1 Description of Devices

Version 3.0

Page 12 of 29

7.1.1 Medtronic Evolut FX System

The Medtronic Evolut FX System is a TAVR implantation system comprised of the following 3 components (Table 1):

- Medtronic Evolut FX TAV
- Medtronic Evolut FX DCS
- Medtronic Evolut FX LS

The system components for the Evolut FX System are shown in Table 1 and detailed descriptions provided in Sections 7.1.2.1, 7.1.2.2 and 7.1.2.3. A summary of features unique to the Evolut FX System is shown in Figure 1.

Table 1. Evolut™ FX System Components

Component	US Model Number	Size (mm)	Aortic Annulus Diameter (range in mm)	
	EVOLUTFX-23	23	18 – 20	
Medtronic Evolut EX TAV	EVOLUTFX-26	26	20 – 23	
Meditonic Evolut FX TAV	EVOLUTFX-29	29	23 – 26	
	EVOLUTFX-34	34	26 - 30	
Evolut FX DCS (18 Fr/14eFr)	D-EVOLUTFX-2329	Used with 23, 26, and 29 mm TAVs	Not applicable	
Evolut FX DCS (22 Fr/18eFr)	D-EVOLUTFX-34	Used with 34 mm TAVs	Not applicable	
Evolut FX LS	L-EVOLUTFX-2329	Used with 23, 26, and 29 mm TAVs	Not applicable	
	L-EVOLUTFX-34	Used with 34 mm TAVs	Not applicable	

Version 3.0

Page 13 of 29

[figure not shown]

Figure 1. Evolut FX System – changes from Evolut PRO+ include radiopaque gold markers for enhanced visualization, a single spine outer shaft, longer and stiffer stability member, flexible capsule, 3 way stopcock, and redesigned tip.

7.1.2.1 Medtronic Evolut FX Transcatheter Aortic Valve

The Medtronic Evolut FX TAV is available in 4 sizes (23, 26, 29, & 34mm), covering an aortic annulus diameter of 18 to 30 mm. For the 26mm and 29mm bioprostheses: If the patient's annulus diameter is within 0.5 mm of the upper or lower bound of the range, use of the larger valve size can be considered, provided additional dimensional criteria as outlined in the Clinical Investigation Plan (CIP) are met. The TAV is comprised of 3 leaflets, a sealing skirt, and outer tissue wrap constructed from glutaraldehyde-fixated porcine pericardium, sewn to a compressible and self-expandable Nitinol support frame, as well as 3 gold radiopaque markers located approximately 3 mm from the inflow of the frame. These radiopaque markers are aligned below the 3 tissue commissure pads, between the inner tissue skirt and the outer tissue wrap, and serve to enhance visualization during implant. The TAV is processed with an anti-mineralization treatment of AOA, a compound derived from oleic acid, a naturally occurring long-chain fatty acid. With the exception of the markers added to the frame, there are no changes to the frame compared to the Evolut PRO+ TAV.

Version 3.0

Page 14 of 29

7.1.2.2 Medtronic Evolut FX Delivery System

The Evolut FX DCS is available in two sizes: 18 Fr and 22 Fr. The 18 Fr FX DCS (hereafter 23-29 mm Evolut FX DCS) is compatible with the Evolut FX 23-29 mm TAVs and the 22 Fr FX DCS is compatible with the Evolut FX 34 mm TAV. The delivery catheter systems are designed to be compatible with commercial 0.035" intravascular wires, and 18 Fr and 22 Fr introducers. The DCS Fr size / TAV compatibility and the compatibility with commercial intravascular wires and introducers is identical to Evolut PRO+. Changes have been made to the tip, capsule, stability member, outer shaft, ILS stopcock and to the handle in order to improve overall ease of use through reduced insertion forces tracking forces of the DCS in tortuous anatomies while preserving stability during deployment.

The DCS consists of a catheter with an integrated handle to assist the user with accurate and controlled deployment. The handle features a gray front grip used to stabilize the system. The deployment knob turns to deploy the bioprosthesis. Arrows on the deployment knob indicate the direction of rotation required to deploy the bioprosthesis. If desired, the deployment knob can be turned in the opposite direction to partially or fully recapture the bioprosthesis if the radiopaque capsule marker band has not yet reached the distal end of the radiopaque paddle attachment. Once the radiopaque capsule marker band reaches the distal end of the radiopaque paddle attachment, it is at the point of no recapture. The deployment knob also features a trigger, which can be engaged to make macro adjustments to the capsule position. The end of the handle features a tip-retrieval mechanism, which can be used to withdraw the catheter tip to meet the capsule after the device has been fully deployed.

7.1.2.3 Evolut FX Loading System

The Evolut FX compresses the bioprosthesis into the catheter. There have been no changes made between the Evolut PRO+ and FX loading systems. This loading system is designed for compatibility with this specific TAV and delivery system.

7.2 Manufacturer

The legal manufacturer and design site of the Evolut FX system is as follows:

Medtronic CoreValve LLC

7.3 Intended Population

The study population includes patients with symptomatic native aortic valve stenosis necessitating valve replacement. Patients who undergo an emergency procedure should not be included in this study.

Version 3.0

Page 15 of 29

7.4 Product Training Requirements

The Evolut FX system will be used within the commercially approved indication in the United States, with exception to any inclusion and exclusion criteria in this protocol, and obtained by the study sites according to standard hospital procedures for commercial products. Local existing approved procedures for commercial product regarding training, distribution, shipment, storage, and handling will be followed. In the event of a device malfunction or explant, refer to the Optimize PRO parent protocol.

7.5 Product Labeling, Tracking, and Accountability

Refer to the Optimize PRO parent protocol for product tracking, labeling, and accountability.

7.6 Product Storage

Sites will follow their institutional standard practice for storing commercial TAVR product.

8 Study Site Requirements

8.1 FX Addendum Site Activation

[figure not shown]
All sites should be activated to the parent protocol prior to, or concurrent with, FX Addendum activation. Full Ethics Committee (EC) or Institutional Review Board (IRB) approval/acknowledgement should be received prior to beginning study activities.

Prior to activation to the addendum, Medtronic will train study site personnel on this clinical investigation plan addendum, and any corresponding changes to the informed consent or data collection and reporting tools. If new members join the study site team, they will receive training on the applicable study requirements relevant to their role before contributing to the study.

Medtronic will provide each study site with documentation of study site/investigator readiness; this letter must be received prior to performing study addendum related activities.

Version 3.0

Page 16 of 29

9 Selection of Subjects

9.1 Study Population

The study population includes patients with symptomatic native aortic valve stenosis that necessitates valve replacement who meet the criteria for on-label use of the Evolut™ FX system in accordance with the Instructions for Use and local regulations.

9.2 Subject Enrollment

This addendum will involve approximately 150 subjects in the US, based on the number of subjects with an attempted TAVR procedure among all active sites. To ensure a widespread distribution of data and to minimize bias in the study results, no site will implant more than 40 subjects without prior authorization from Medtronic. Subjects who exit from the study after implantation will not be replaced.

9.3 Inclusion Criteria

Prospective subjects must meet all of the following inclusion criteria to be eligible for participation:

- Acceptable candidate for treatment with the Evolut™ FX system in accordance with the commercial Instructions for Use and local regulations
- 2. Subject is symptomatic from his/her aortic valve stenosis, as demonstrated by New York Heart Association (NYHA) Functional Class II or greater
- 3. Subject and the treating physician agree that the subject will return for all required post procedure follow-up visits
- 4. Anatomically suitable for transfemoral TAVR with the Medtronic TAVR system
- 5. Subject meets the legal minimum age to provide Informed Consent based on local regulatory requirements

9.4 Exclusion Criteria

Subjects are not eligible for study participation if they meet ANY of the following exclusion criteria:

- 1. Contraindicated for treatment with the Evolut™ FX system in accordance with the commercial Instructions for Use
- 2. Anatomically not suitable for the Evolut™ FX system
- 3. Previous aortic valve replacement
- Reduced ventricular function with left ventricular ejection fraction (LVEF) < 35% as measured by resting echocardiogram
- Frailty assessments identify:

Version 3.0

Page 17 of 29

[figure not shown]

- o Subject is <80 years of age and three or more of the following apply; OR subject is ≥ 80 years of age and two or more of the following apply
 - Wheelchair bound
 - Resides in an institutional care facility (e.g., nursing home, skilled care center)
 - Body Mass Index <20kg/m²
 - Grip strength <16kg
 - Katz Index score ≤4
 - Albumin <3.5 g/dL
- 6. Bicuspid valve verified
- 7. Aortic root angulation (angle between plane of aortic valve annulus and horizontal plane/vertebrae) > 70°
- 8. Implanted with pacemaker or ICD
- 9. Prohibitive left ventricular outflow tract calcification
- 10. Estimated life expectancy of less than 12 months due to associated non-cardiac co-morbid conditions
- 11. Other medical, social, or psychological conditions that in the opinion of the Investigator precludes the subject from appropriate consent or adherence to the protocol required follow-up exams
- 12. Currently participating in an investigational drug or another device trial (excluding registries)
- 13. Need for emergency surgery for any reason
- 14. Subject is less than legal age of consent, legally incompetent, or otherwise vulnerable*.

^{*} Notes: Vulnerable subjects include individuals whose willingness to volunteer in a clinical investigation could be unduly influenced by the expectation, whether justified or not, of benefits associated with participation or of retaliatory response from senior members of a hierarchy in case of refusal to participate. EXAMPLE: Individuals with lack of or loss of autonomy due to immaturity or through mental disability, persons in nursing homes, children, impoverished persons, subjects in emergency situations, ethnic minority groups, homeless persons, nomads, refugees, and those incapable of giving informed consent. Other vulnerable subjects include, for example, members of a group with a hierarchical structure such as university students, subordinate hospital and laboratory personnel, employees of the sponsor, members of the armed forces, and persons kept in detention. (2)

Version 3.0

Page 18 of 29

10 Study Procedures

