11.2 Potential Benefits

Participation in this clinical study will not result in any direct benefit to the patient. Trial subjects implanted with an Evolut™ FX device receive the same medical treatment as if they were not participating in this post-market study. Participation contributes to expansion of the knowledge base with respect to the use of the Evolut™ FX system in a routine hospital setting.

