8.1. Study Subjects

8.1.1. Disposition of Subjects

Subjects disposition will be summarized, including the number of subjects enrolled, attempted implant, implanted, died, withdrawn, lost-to follow up, and completed each scheduled follow up visit during the study.

Clinical Investigation Plan (CIP) Deviations 8.1.2.

Protocol deviations will be reported regardless of whether medically justifiable, pre-approved by Medtronic, or taken to protect the subject in an emergency. CIP deviations will be summarized by follow up visit.

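### Does exclusion 14 bar whole groups, such as ethnic minority patients or nursing-home residents, on membership alone?

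*Protocol*

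**What the plan says.** Section 9.4 of the Protocol makes a patient ineligible on meeting any one exclusion. Three of the exclusions matter here.

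- **Criterion 14:** "Subject is less than legal age of consent, legally incompetent, or otherwise vulnerable". An asterisk leads to a note.
- **Criterion 5 (frailty):** "Resides in an institutional care facility (e.g., nursing home, skilled care center" is one of six items. Exclusion needs three or more items below age 80, and two or more from age 80.
- **Criterion 11:** "Other medical, social, or psychological conditions that in the opinion of the Investigator precludes the subject from appropriate consent", or from keeping to the required follow-up.

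The note to criterion 14 begins with a test: "Vulnerable subjects include individuals whose willingness to volunteer in a clinical investigation could be unduly influenced by the expectation" of benefit or of retaliation for refusing. It then lists groups under the label EXAMPLE, including "persons in nursing homes, children, impoverished persons, subjects in emergency situations, ethnic minority groups, homeless persons, nomads, refugees". A second list, introduced as examples of people in hierarchical groups, follows. The note ends with a citation to ISO 14155:2011, reference 2 in section 17.

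The synopsis (section 3) repeats criterion 14 among the key exclusions without the note. SAP section 6.3.4 carries the same criterion and note for the parent study. Sections 10.1.1 and 10.1.7 send screening, enrolment and consent to the parent protocol, which is not among the documents reviewed.

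**The concern.** The note supplies both a test and a list but does not say which one a site applies. Because the exclusions operate singly, a coordinator could treat the list as a checklist. An ethnic minority patient, a patient with little money or a nursing-home resident would then be turned away despite being able to give free consent, and nothing about the device would justify it.

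Three things would be at stake.

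- **Who the results describe.** Section 11.2 says that the study adds knowledge of the "FX system in a routine hospital setting". A case mix narrowed on social grounds would fit that aim less well.
- **Consistency.** Section 6 names screening against pre-defined criteria as a measure against bias. About 10 sites could apply a criterion with two readings in different ways.
- **Visibility.** SAP section 8.1.1 states: "Subjects disposition will be summarized, including the number of subjects enrolled, attempted implant, implanted, died, withdrawn" and so on. It starts at enrolment and names no count of screening failures, so patients turned away before consent would not appear.

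Criterion 5 seems to sharpen the point, since it tolerates nursing-home residence on its own and a literal criterion 14 does not.

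**Working it through.** No sample size, power or error rate depends on this criterion, and the plan states no figure to reproduce. The check is a reading of the text, plus two small counts.

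**1. Which reading fits the note?**

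| Feature of the text | Membership alone excludes | Each person is judged |
|---|---|---|
| Opens with an undue-influence test | Test has no work to do | Test is the rule |
| Groups labelled as examples, in both lists | Examples become a checklist | Examples illustrate the test |
| Cites an ISO standard | Neutral | Fits a borrowed definition |
| Repeats children and people who cannot consent, already covered by criterion 14 | Redundant | Fits a borrowed definition |
| Nursing-home example in criterion 5 | Has no effect | Has effect |

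**2. Nursing-home residents under criteria 5 and 14.** A resident already meets 1 of the 6 frailty items.

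- Aged 80 or over: excluded at 2 items, and 2 − 1 = 1, so the resident passes criterion 5 with 0 other items.
- Under 80: excluded at 3 items, and 3 − 1 = 2, so the resident passes with 0 or 1 other items.

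A literal criterion 14 would exclude all of these residents, and the nursing-home example in criterion 5 would decide nothing. A reading that leaves both criteria with a function is the better one. Nor do the two contradict each other: criterion 5 counts frailty, criterion 14 protects consent, and independent exclusions may overlap.

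**3. Can the effect be sized from the list?** The note names 10 groups in its first list and 5 in its second, 15 in all. Three are defined by age or capacity: loss of autonomy, children, and people incapable of consent. That leaves 15 − 3 = 12, and 12/15 = 80%. This is a share of phrases, not of patients. It also depends on parsing: if the five hierarchical examples count as one category, the share is (12 − 4)/(15 − 4) = 8/11 = 73%. And the 12 include detained persons and sponsor employees, for whom pressure to volunteer is a real worry.

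**4. What could change in the results?** Let *f* be the fraction of otherwise eligible candidates kept out, *p*_out their event rate and *p*_in the rate in those enrolled. The rate in all candidates is (1 − *f*)·*p*_in + *f*·*p*_out, so it differs from the reported rate by *f*·(*p*_out − *p*_in). The documents give neither *f* nor *p*_out. Enrolment is fixed at about 150 attempted implants (sections 9.2 and 13.4), so precision is unaffected. Section 13.3 rules out hypothesis testing, so no decision depends on the difference.

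**The case for a change.** The strongest opposing argument is that the literal reading is not far-fetched. The first two limbs of criterion 14 already cover legal age and legal incompetence, and criterion 11 covers conditions that prevent proper consent. Much of what the word vulnerable adds may therefore seem to be the groups defined by circumstance. The synopsis gives no test at all. Protective reasons for a blanket bar are also weak, since sections 11.1 and 11.2 say that subjects receive the same treatment as outside the study, with the post-procedure CT as the only added risk. A site that enrolled a listed patient under one reading would record a deviation under the other.

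Part of this stands: the documents contain no explicit rule, and the SAP's copy of the parent criteria adds none. The rest does not carry the point.

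- Under the individual reading the word vulnerable still does something: it reaches competent adults under pressure to take part, such as subordinate staff.
- A list of key criteria in a synopsis ordinarily omits footnotes, and section 9.4 governs.
- Section 7.4 discloses that use is on-label "with exception to any inclusion and exclusion criteria in this protocol", so a narrower population is declared. The phrase about routine hospital use comes from a statement of benefits and does not claim representativeness.
- The disposition list in SAP section 8.1.1 is introduced as non-exhaustive. Enrolled means consent signed (SAP section 8.1.3), so exclusions after consent would show as a gap between enrolled and attempted, though without the reason.

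One uncertainty remains. The parent protocol's screening and consent sections could hold a rule that supports either reading.

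**Conclusion.** This is an unwritten rule that sites can fill sensibly, and the plan can stand. The note's opening test, its labelled examples, its cited source and the nursing-home item in criterion 5 all favour judging each patient. Harm arises only under the literal reading, and nothing in the documents shows that reading in use.

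The number of patients affected is unknown. At most, the case mix of about 150 patients could shift; no stated statistic, test or threshold would change.

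Rewriting the criterion would bring little gain and some cost. Declaring that no listed group is excluded by membership would extend to detained persons and sponsor employees, a subject-protection choice that belongs to the sponsor and the ethics committee. It would also leave the addendum at odds with the matching criterion in SAP section 6.3.4 until the parent plan, which governs under section 4.1, was amended too.

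The conclusion rests on two assumptions: that sites apply the note's test to the individual, and that the parent protocol contains no instruction to exclude by group.
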